5.6.1 Primary endpoint

The primary efficacy endpoint is based on the blinded raters' Clinical Impression of Change in Severity (CI-CS) score over 6 weeks determined by comparing videos showing the patient's performance on a pre-defined anchor clinical symptom scale: either the 9 Hole Peg Test of the Dominant Hand (9HPT-D) or the 8 Meter Walk Test (8MWT).

For each patient, there will be two CI-CS scores. These two scores indicate the level of change in severity observed in Visit 4 (end of treatment) compared to Visit 2 (baseline) and the level of change in severity observed in Visit 6 (end of washout) compared to Visit 4 (end of treatment). Both CI-CS scores are measured on a 7-point Likert-point scale (-3 = significantly worse to +3 = significantly improved, see Section 5.2 for the precise definition) and the primary endpoint is defined as the difference between both CI-CS scores.

The primary endpoint will be summarized using descriptive statistics, including a frequency table, and frequency percentages will be presented graphically using a bar chart. The primary statistical analysis will be performed using a one-sample t-test comparing the CI-CS difference score to zero. Statistical output will present the number of patients included in the analysis, both CI-CS scores, the mean of the difference, the corresponding two-sided 90% confidence interval, and a one-sided p-value.

The assumption of normality will be visually checked and if the assumption does not hold, a Wilcoxon signed-rank test will be performed instead of the t-test using the difference score. Statistical output will then present the number of patients included in the analysis, both CI-CS scores, the (pseudo-) median of the difference using the Hodges-Lehmann estimator, the corresponding two-sided 90% confidence interval, and a one-sided p-value.

Clinical Study Reference: IB1001-202

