Each video pairing (CI-CS) will be read by the two independent raters, and the appropriate Likert scale score will be entered onto the eCRF. If there is a difference of one (1) point in the two primary blinded reviewers' CI-CS scores for a specific video pairing, the two scores will be averaged. If there is difference greater than one (1) point between the two primary blinded reviewers' CI-CS scores for a specific video pairing, an adjudication read will be triggered. In such cases, a third blinded reviewer will review the scores given from each of the two primary independent reviewers and determine which score is more accurate, that of reviewer A or reviewer B (adjudication by consensus). The adjudicator's decision will be the final score for that video assessment.

The statistical analysis of this endpoint will utilize a single sample t-test comparing the mean value of the primary endpoint with zero. This endpoint allows the effect N-Acetyl-L-Leucine to be measured both in terms of improvement during treatment followed by any deterioration once treatment is removed.

Summary statistics will in addition be calculated separately according to subgroups defined by the primary anchor test

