8.5.2 Secondary Efficacy Endpoints

A key Secondary Endpoint that will be evaluated to directly supplement the analysis of the primary endpoint is based on the independent raters' Clinical Impression of Severity (CI-S) of each video.

The independent raters will be given 6 videos of the patient's performance of the primary anchor test taken at Visit 1 to Visit 6. The videos will be labeled as Video A, B, C, D, E, F. The videos will be presented in a random order, and the independent raters will be blinded to the timepoint corresponding to each video.

For each video, the independent raters will make their evaluation of the CI-S, which asks: "Considering your total clinical experience with this particular population, how ill is the patient at this time?"

The CI-S is rated on a 7-point Likert scale ranging from + 3 (normal, not at all ill) to -3 (among the most extremely ill patients). For the CI-S, if there is one (1) point or more difference in the two blinded reviewers scores, the two scores will still be averaged.

Supportive secondary endpoints will be evaluated that directly supplement the analysis of the primary endpoint as follows:

- The CI-CS for end of treatment with N-Acetyl-L-Leucine (Visit 4) versus baseline (Visit 2) and end of washout (Visit 6) versus end of treatment with N-Acetyl-L-Leucine (Visit 4) will each be summarized descriptively.
- Improvement in the primary and non-primary anchor test measures will be evaluated based on the change in the blinded raters' Clinical Impression of Severity (CI-S) between baseline (average for Visit 1 and Visit 2) and end of treatment with N-Acetyl-L-Leucine (average for Visit 3 and Visit 4) minus the change in CI-S between end of treatment with N-Acetyl-L-Leucine (average for Visit 5 and Visit 6). Statistical testing for the primary anchor test CI-S endpoint will be as for the primary endpoint. There will be no formal statistical testing of the non-primary test.

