- Treating Physician Clinical Global Impression of Change (CGI-C) comparing end of treatment (Visit 4) to baseline (Visit 2), and end of washout (Visit 6) to end of treatment (Visit 4)
- Caregiver Clinical Global Impression of Severity (CGI-S) at every visit
- Caregiver Clinical Global Impression of Change (CGI-C) comparing end of treatment (Visit 4) to baseline (Visit 2), and end of washout (Visit 6) to end of treatment (Visit 4)
- Patient Clinical Global Impression Scales Impression of Severity (CGI-S) at every visit *if they are able*
- Patient Clinical Global Impression of Change (CGI-C) comparing end of treatment (Visit 4) to baseline (Visit 2), and end of washout (Visit 6) to end of treatment (Visit 4) *if they are able*

The SARA total score, the SCAFI total score, the individual SCAFI subtests: 9 Hole Peg Test with the Dominant Hand (9HPT-D), 8 Meter Walk Test (8MWT), and PATA test, will be evaluated statistically based on a single sample t-test or a single sample Wilcoxon Signed Rank test.

The individual SCAFI subtest: 9 Hole Peg Test with Nondominant hand (9HPT-ND), and the mDRS will be evaluated descriptively.

The CGI-S measures, and caregiver and patient CGI-C measures will be summarized descriptively. The physician's CGI-C measures will be analyzed as for the CI-CS primary endpoint.

The measures of the two indices (-5L and -Y) of the EQ-5D descriptive system and measures of the two indices (-5L and -Y) of the EQ-5D visual analogue scale (VAS) will be evaluated descriptively.

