8.10 Determination of Sample Size

It is postulated that N-Acetyl-L-Leucine will show effectiveness in 30% of patients and this success rate is viewed as being clinically important. Assuming that this group of patients will have scores that are evenly distributed across the values 1 and 2 for the primary endpoint and further that the remaining 70% of patients will have scores that are evenly distributed between the values -1, 0, and 1. The resulting mean score is 0.45 and the standard deviation (SD) for the primary endpoint under these assumptions is then 1.02. With 30 patients reporting on the primary endpoint, the study will have 76% power to detect a treatment benefit in a 5% one-sided one-sample t-test.

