5 PARENT STUDY: STATISTICAL ANALYSIS

5.1 General considerations

The Parent study is considered the study period between screening (Visit 0 or Visit 1) through Visit 6.

Raw data (in listings) will be presented in the same precision as received. Appropriate rounding will be performed for the following summary statistics, where applicable: mean, standard deviation (SD) and two-sided 90% confidence limits will be presented with at least one more decimal than the original data; minimum and maximum values will be presented with the same precision as the original data. In frequency tables, percentages will be presented with 1 decimal unless otherwise stated.

P-values will be presented with 3 decimals, and those smaller than 0.001 will be replaced by <0.001. One-sided p-values smaller than 0.05 will be considered statistically significant for the primary endpoint and indicative for other endpoints. No adjustment for multiple comparisons will be applied. Conclusions regarding treatment efficacy will not solely rely on detecting statistical significance but equal emphasis will be placed on the magnitude and clinical relevance of treatment differences as judged by the point estimates. All evaluations other than the primary endpoint will be considered exploratory in nature.

Descriptive statistics presented in general summary tables will be the number of non-missing observations (n), mean, SD, minimum, median and maximum for quantitative data. For categorical data, frequency counts and percentages will be determined.

In general, baseline is defined as the value measured prior to first study treatment administration (at Visit 2), unless otherwise specified. In case no value at Visit 2 is available, the value measured at Visit 1 will be used. A footnote may be added to those tables/listings presenting baseline value, with an explanation how this value was assessed.

If available in the database, data for screening failures will not be presented in summary tables, except for disposition, medical history and end-of-study displays. Data for screening failures will be listed as available.

A treatment emergent adverse event (TEAE) is defined as an adverse event that appears during or after study treatment and was absent before.

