7 CHANGES TO PROTOCOL AND OTHER RELEVANT REMARKS

Instead of Bland-Altman analyses of outcome scores at Visit 1 vs Visit 2, Visit 3 vs Visit 4, and Visit 5 vs Visit 6 as described in the protocol for the Parent study, an ICC method for agreement

Clinical Study Reference: IB1001-202

between the visits will be used instead to assess the stability of the outcome, as described in section 5.6.4. This is because no per-rater information is available in the dataset to be received, only an averaged or agreed value.

Regarding CI-S, the protocol is stating that for each assessment, the videos will be labeled as Video A, B, C, D, E, F. This is however not present in the DTA and test data from and is therefore removed from the SAP.

For Quality-of-Life measures, since the scoring is done for children with the EQ-5D-Y and for adults with the EQ-5D-5L, tabulations and analyses will be done separately for the corresponding age groups. The presentations on the VAS will be combined for children and adults.

For the Parent phase, sparse PK sampling will be collected for biochemical analysis to characterize the pharmacokinetics of N-Acetyl-L-Leucine in patients with GM2 Gangliosidosis. For the Extension phase, full PK profiles will be collected at Visit 7 and Visit 9. Creation of descriptive displays and reporting of these data is outside the scope of this statistical analysis plan. PK concentration data and PK parameters (following a population PK analysis) will be included in SDTM domains, after receipt. For the Parent phase a listing of PK concentration data will be created for inclusion in the Parent phase CSR, since the full PK report will only be available after the end of the Extension phase. Furthermore, urine tests for N-Acetyl-D-Leucine are handled by the same lab but will be included in the clinical database and will therefore be part of the CDISC datasets.

Regarding the sensitivity analysis (imputation of value -1) for missing data in the primary and secondary analyses: this is only applied to the primary analysis of the Parent phase. Regarding the LOCF/assumption of value 0 for missing data: this is only applied to the primary and one key secondary endpoint as specified in the relevant sections in this SAP.

The investigation of the intra-rater correlation cannot be performed, since the **sector** data do not differentiate the data per rater but rather provide an average or agreed value. Therefore, this analysis has been removed from the SAP.

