11.3 End-of-text tables and graphs

Following ICH E3 guidelines, all tables and graphs mentioned here will be presented in Section 14 of the CSR, and tables will be prepared in the order and with section number as stated.

Table/graph number	Contents of table/graph
14.1 Demographic	e Data Summary figures and tables
14.1.1-14.1.4	Demographics (ITT, mITT, PPS and SAF population)
14.1.5-14.1.7	Baseline characteristics (ITT, mITT and PPS population)
14.1.7	Disposition
14.1.8	Medical history
14.1.9	GM2 Gangliosidosis specific history
14.1.10	Compliance
14.2 Efficacy Data	summary figures and Tables
14.2.1	Result of t-test or Wilcoxon test on the primary endpoint (mITT and PPS), including sensitivity analysis (only mITT).
14.2.2	Frequency table of the CI-CS score Visit 4 vs Visit 2 minus the CI-CS score Visit 6 vs Visit 4, combined with the frequency table of the CI-CS score Visit 4 vs Visit 2 and separately, the CI-CS score Visit 6 vs Visit 4 (mITT and PPS population)
14.2.3	Descriptive statistics of the CI-CS score Visit 4 vs Visit 2 minus the CI-CS score Visit 6 vs Visit 4, combined with the descriptive statistics of the CI-CS score Visit 4 vs Visit 2 and separately, the CI-CS score Visit 6 vs Visit 4 (mITT and PPS population).
14.2.4	Bar chart of CI-CS score Visit 4 vs Visit 2 minus CI-CS score Visit 6 vs Visit 4 (mITT and PPS population)
14.2.5	Frequency table of the CI-CS score Visit 4 vs Visit 2 minus the CI-CS score Visit 6 vs Visit 4 according to subgroups, combined with the frequency table of the CI-CS score Visit 4 vs Visit 2 and separately, the CI-CS score Visit 6 vs Visit 4 according to subgroups (mITT population)
14.2.6	Descriptive statistics of the CI-CS score Visit 4 vs Visit 2 minus the CI-CS score Visit 6 vs Visit 4 according to subgroups, combined with the descriptive statistics of the CI-CS score Visit 4 vs Visit 2 and separately, the CI-CS score Visit 6 vs Visit 4 according to subgroups (mITT population)
14.2.7	Bar chart of CI-CS score Visit 4 vs Visit 2 and separately, CI-CS score Visit 6 vs Visit 4 (mITT and PPS population)
14.2.8	Pearson rank correlation coefficients (mITT population)
14.2.9	ICC analysis (mITT population)

14.2.10	Result of t-test or Wilcoxon test on the key secondary endpoint 'Change in severity score based on averaged CI-S' (mITT and PPS population),

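### SAP 5.6.1 lets an undefined visual normality check replace the protocol's only primary test and its mean, and SAP Section 7 does not record the change

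*SAP*

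**What the plan says.** Protocol 8.5.1, for the primary endpoint: "The statistical analysis of this endpoint will utilize a single sample t-test comparing the mean value of the primary endpoint with zero". No alternative is named, and the synopsis repeats the same test. Protocol 8.10 rests the sample size on it: "the study will have 76% power to detect a treatment benefit in a 5% one-sided one-sample t-test".

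Where the protocol wants a choice of test, it says so. In 8.5.2 the SARA total, SCAFI total and named SCAFI subtests "will be evaluated statistically based on a single sample t-test or a single sample Wilcoxon Signed Rank test". For CI-S the protocol instead ties the method to the primary analysis: "Statistical testing for the primary anchor test CI-S endpoint will be as for the primary endpoint". The physician CGI-C is tied to it in the same way.

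SAP 5.6.1 starts from the t-test and then adds: "The assumption of normality will be visually checked and if the assumption does not hold, a Wilcoxon signed-rank test will be performed instead". After a switch, the statistical output shows a Hodges-Lehmann pseudo-median with a two-sided 90% interval and a one-sided p-value, in place of the mean and its interval. Table 14.2.1 in SAP 11.3 is planned as the result of one test or the other, not both.

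SAP Section 7 lists departures from the protocol, including a change of method for an exploratory reliability analysis ("Instead of Bland-Altman analyses of outcome scores at Visit 1 vs Visit 2", an intraclass correlation is used). It has no entry for the primary test. SAP Section 1 states that the plan agrees with protocol version 7.0.

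**The concern.** The fallback is specified, but the trigger is not. The SAP does not say which plot is read, what counts as failure, who decides, or when. The Blinded Data Review Meeting (SAP 3.4) is meant to be blind to outcome data where possible, so it is not an obvious place for the check.

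Under SAP 5.2, rater scores one point apart are averaged without rounding. The primary score, a difference of two such values, therefore lies on a half-point grid and cannot be strictly normal. Whether the assumption holds becomes a matter of how strictly one reads the plot. In a single-arm trial an uncentred plot of this score also shows the treatment effect.

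Two things depend on the reading. SAP 5.1 says: "One-sided p-values smaller than 0.05 will be considered statistically significant for the primary endpoint and indicative for other endpoints", so the choice of test decides which p-value is the primary result. SAP 5.1 also gives point estimates equal emphasis with significance, and the switch changes the estimate from a mean to a pseudo-median. Two competent analysts could report different primary results from the same data.

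**Working it through.** **1. The plan's own power figure.** Protocol 8.10 puts 30% of patients evenly on 1 and 2, and 70% evenly on -1, 0 and 1. The probabilities are 0.233 at -1, 0.233 at 0, 0.383 at 1 and 0.150 at 2.

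- Mean = -0.233 + 0.383 + 2(0.150) = 0.45, as stated.
- Variance = (0.233 + 0.383 + 4 × 0.150) - 0.45² = 1.217 - 0.2025 = 1.014, so SD = 1.007. With divisor n-1 at n = 30 it is 1.024, against the stated 1.02.
- Noncentrality = (0.45/1.02) × √30 = 2.42. With 29 degrees of freedom and one-sided 5%, power is 76.3%, against the stated 76%. The figure reproduces.
- At the planned mITT size of 36: (0.45/1.02) × 6 = 2.65, power 82.9%.

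**2. How far the trigger is open.** Under this distribution, two stand-ins bracket the visual check. Neither is in the SAP.

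- Strict (Shapiro-Wilk at 5%): normality fails in all 5,000 simulated trials, at n = 30 and at n = 36.
- Lenient (sample skewness beyond ±1): fails in 0.12% of trials at n = 30 and 0.03% at n = 36.

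**3. Effect on the result under the plan's distribution.** 20,000 simulated trials per run, one-sided 5%, zeros dropped. The ranges cover two sets of runs that compute the Wilcoxon p-value differently (tie-corrected normal approximation throughout, or exact when 20 or fewer scores are non-zero).

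| n | t-test significant | Wilcoxon significant | Verdicts differ |
|---|---|---|---|
| 30 | 76.3% to 77.0% | 77.8% to 78.5% | 1.6% to 1.7% |
| 36 | 83.4% to 83.5% | 84.7% to 85.1% | 1.4% to 1.6% |

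Nearly all the disagreement is Wilcoxon significant and t-test not. The Hodges-Lehmann estimate averages 0.46 but is coarse. In 4,000 trials at n = 30 it took only the values 0 (693, 17%), 0.5 (2,902, 73%) and 1.0 (405, 10%), against a true mean of 0.45.

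**4. Symmetric nulls (assumed; four shapes, n = 36).** At least one of the two tests is significant in 4.8% to 6.0% of trials, so even choosing the better p-value gains little.

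**5. Right skew (assumed, n = 36).**

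| Distribution | Verdicts differ | t-test only | Mean / Hodges-Lehmann |
|---|---|---|---|
| 30% at 3 to 4, rest as plan non-responders | 3.2% | 3.2% | 1.05 / 0.99 |
| 20% at 3 to 4, rest uniform on -2 to 2 | 4.7% | 3.8% | 0.70 / 0.67 |
| 20% at 3 to 4, rest on -1, 0, 1 | 11.6% | 11.6% | 0.70 / 0.53 |
| 20% at 3 to 4, rest on -0.5, 0, 0.5 | 20.0% | 20.0% | 0.70 / 0.32 |
| 20% at 3 to 4, rest on -1 to 1 in half points | 21.6% | 21.6% | 0.70 / 0.48 |
| 20% at 3 to 4, rest averaging -0.41 | 27.7% | 27.7% | 0.36 / -0.05 |

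Here switching loses a result that the protocol's test would give.

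**6. Left-skewed nulls with mean zero (assumed, n = 36), false-positive rates.**

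| Values (probabilities) | t-test | Wilcoxon |
|---|---|---|
| -2, -1, 0, 1 (.1, .1, .5, .3) | 6.8% | 6.4% |
| -2, 0, 1 (.15, .55, .3) | 7.2% | 6.3% |
| -3, -1, 0, 1 (.05, .15, .5, .3) | 8.6% | 12.3% |
| -2, -1, 0, .5, 1 (.1, .1, .3, .4, .1) | 8.0% | 13.9% |
| -3, 0, 1 (.1, .6, .3) | 9.3% | 19.9% |

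Under skew the Wilcoxon test no longer addresses the mean, which is the quantity the protocol tests.

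**The case against.** The SAP keeps the t-test as the default and writes out the fallback test, estimator, interval and p-value in advance. The mean and SD of the score still appear in Table 14.2.3, so anyone can recover the t statistic as mean/(SD/√n), and a favourable switch could not be hidden. Significance is only a guide in Protocol 8.2. On the plan's own inputs the verdict hardly changes, and the large discrepancies come from distributions that are not in the documents. Shapiro-Wilk is not a visual check, and the planning distribution is nearly symmetric (skewness about -0.11). A centred Q-Q plot would not reveal the effect. The t-test is itself liberal in the left-skewed nulls, and in two of the five Wilcoxon is closer to 5%. An objective trigger with a Section 7 entry would also be a remedy.

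Most of this stands as a limit on the size of the problem, and the claim that the plot shows the effect applies only to an uncentred plot. It does not close the gap. Being able to recompute both results does not settle which one is primary. The near-symmetry of the planning distribution does not tell an analyst whether a four-value score counts as normal. A formal trigger is the weaker remedy: a standard normality test would reject a score this coarse almost every time, and the primary test would still depend on the data. Replacing the test and estimator is a change to the protocol, and the SAP has a section for recording changes.

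**Conclusion.** The point holds. The protocol fixes one primary test. The SAP makes both the test and the estimate depend on a visual judgement with no stated criterion, and Section 7 does not record the change.

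The numerical consequence is limited: disagreement in 1.4% to 1.7% of trials under the plan's distribution, and almost no inflation under symmetric nulls. It becomes material only under marked skew, and those figures rest on assumed distributions. The strict and lenient stand-ins for the check are also assumptions; they show that the trigger is open, not how a particular reader would behave. The plan should be changed because the correction is nearly free, but the priority is minor to moderate.

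**What to change.** Replace the conditional rule in SAP 5.6.1 with a fixed one, for example:

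> The primary analysis is the one-sample t-test, reporting the mean difference, its two-sided 90% confidence interval and a one-sided p-value, whatever the distribution of the scores. The Wilcoxon signed-rank test, with the Hodges-Lehmann estimate and its two-sided 90% confidence interval, is always reported as a supportive analysis.

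Make Table 14.2.1 show both results. Apply the same rule to the averaged CI-S difference (SAP 5.6.2, Table 14.2.10) and the physician CGI-C difference (SAP 5.6.3, Table 14.2.57), which the protocol ties to the primary analysis. In the forest plots, the choice between mean and pseudo-median then resolves to the mean for the primary endpoint. Table 14.2.58 tests the CGI-C periods separately and is a different matter.

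The primary test then matches the protocol, so no Section 7 entry is needed for it. The change should be made before database lock. The documents do not say whether the parent-study lock has passed; if it has, the study report should treat the t-test as primary and show both.

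The cost is SAP wording and one supportive output per endpoint, with no change to data collection or sample size. Power stays at 76.3% for n = 30 and 82.9% for n = 36. Under the planning distribution this gives up about 1.5 points of power against Wilcoxon, and the t-test's mild liberality in the assumed left-skewed nulls (about 7% to 9%) remains.
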